1. CLINICAL PROTOCOL

1.1 Background

Recent studies have shown that inflammation plays an important role in the pathogenesis of Dry Eye Disease (DED). Ocular surface inflammation often exacerbates the subject's signs and symptoms, and results in an increase in the immune cells and other inflammatory mediators located in the ocular surface. Dry eye disease is one of the most commonly encountered ophthalmic disorders. It is a multifactorial disease of the ocular surface and tear film, characterized by symptoms of eye irritation, tear instability and vision impairment. Despite being very common, standardized therapy is not available.

Due to the underlying inflammation associated with DED, anti-inflammatory steroid medications are used for the treatment of DED. "Soft steroids" are often preferred because their chance of increasing intraocular pressure (IOP) is lower than other steroids. One of the "soft steroids" that is commonly used for the treatment of inflammation associated with ocular surface disease is loteprednol etabonate 0.5% ophthalmic suspension (Lotemax, Bausch & Lomb, Inc).

Current steroid therapy in DED is comprised of pulse therapy (to avoid adverse events associated with long-term steroid use) of usually 2 weeks duration, administered BID. This timeframe is often too short to meaningfully resolve the inflammation associated with DED. More recently steroid treatment of at least 6 weeks with tapered dosing has been advocated.

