5.2 Study Drug/Device Compliance/Adherence

Directed questioning using the (Ocular Tolerability and Compliance Questionnaire – Appendix I) will be administered by the investigator or research staff. Results on the participants' compliance and adherence to the study protocol and study drug will be recorded on the paper case report form (CRF) at the second and third visits (2 and 6 weeks after enrollment).

Subjects will not be withdrawn for lack of compliance with the study drug regimen.

During the study, all concomitant medication treatment regimens, ocular hygiene treatments (i.e., lid scrubs and warm compresses), or insertion of punctal plugs will be kept constant as permitted by accepted medical practice. If one of the aforementioned treatment regimens needs to be modified, the participant may be withdrawn based on the investigator's discretion.

Additionally, if there is an administration of a prohibited medication (including any other steroid) or procedure (any ocular surgery), the participant may be withdrawn based on the investigator's discretion.

Participants must be compliant with IVCM imaging on at least 2 of their 3 visits or they will be withdrawn. Subjects who are withdrawn may be replaced by new enrolled subjects to maintain the sample size in each group.

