5.5 Other Medications

Administration

The use of any concurrent, prescription, or over-the-counter medication, is to be recorded along with the reason the medication was taken. During the study, all concomitant medication treatment regimens, ocular hygiene treatments (i.e., lid scrubs and warm compresses), or insertion of punctal plugs will be kept as constant as permitted by accepted medical practice.

Using artificial tears (preserved and non-preserved) are permissible at the screening visits and during the study. However, concomitant use of artificial tears will be monitored. At each study visit, subjects will be queried about the average number of times they used artificial tears each day during the past week and the number of days during the past week when they did not use any artificial tears.

Systemic and topical ophthalmic medications, that the subjects are already taking as part of their current treatment for dry eye disease will be maintained, without a change in frequency.

When necessary, treatment and administration of any other therapy, besides their current and study's regimen, will be done as the safety of the study participant is the primary consideration. The administration of a prohibited medication or procedure will be considered a protocol violation and the subject may be discontinued from the study. Prohibited medications include other ophthalmic steroids. Prohibited procedures include any ocular surgery.

• Rescue Medication or Therapy

When necessary, administration of any other therapy besides the study medication and their current medications will occur for the safety of the subject, which is the primary concern. If treatment with artificial tears is inadequate, or if the subject develops a severe form of ocular surface disease and dry eye, the subject may be unmasked by the investigator. To ensure the subject's safety and proper treatment, unmasking of the study treatment assignment will allow the investigator to institute appropriate follow-up care. The subject will be kept in the study so that we can do an "intention to treat" analysis.

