7.7 Early Termination

If a subject withdraws or is withdrawn from the study prior to completion of all study visits, there will be no additional procedures performed

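### Withdrawal rules end collection of the week-6 data that the intention-to-treat primary analysis needs, and only an optional imputation covers the gap

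*Combined protocol and SAP*

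**What the plan says.** **Analysis.** Section 10.5 calls for a standard ITT primary analysis, with every participant counted in the assigned arm. It says that non-compliant subjects who stay active will be followed for this purpose. Its only provision for missing data is that a secondary analysis may impute some variables; it names no variable and no method. Section 10.4 (Analysis Population) reads N/A.

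**Grounds for withdrawal.**
- Concomitant regimen change, section 5.2: "If one of the aforementioned treatment regimens needs to be modified, the participant may be withdrawn", at the investigator's discretion.
- Prohibited treatment, section 5.5: "The administration of a prohibited medication or procedure will be considered a protocol violation and the subject may be discontinued from the study". Section 5.2 says the same and adds that it is discretionary. Section 5.5 also states: "Prohibited medications include other ophthalmic steroids".
- Missed imaging, section 5.2: a subject with IVCM at fewer than 2 of the 3 visits is withdrawn. This one is mandatory.
- Drug non-compliance, section 5.2: "Subjects will not be withdrawn for lack of compliance with the study drug regimen". Section 10.5 instead leaves this to the investigator.

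**After withdrawal.** Section 7.7: "there will be no additional procedures performed". Sections 8.1 and 9.3 continue follow-up only until an adverse event resolves.

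**Replacement.** Section 5.2: "Subjects who are withdrawn may be replaced by new enrolled subjects to maintain the sample size in each group".

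**Limiting text.** For inadequate control or severe disease, where the investigator may unmask, section 5.5 says "The subject will be kept in the study so that we can do an" ITT analysis. Section 8.1 repeats this.

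**The concern.** An ITT analysis needs outcomes as well as assignments. A subject withdrawn before week 6 stays in the ITT set by name but has no week-6 value, and the plan does not say how the primary comparison deals with that.

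The loss need not be random. A concomitant regimen may be changed because the eyes are doing badly or well. Another ophthalmic steroid may be started for the same reason: section 1.1 notes that "anti-inflammatory steroid medications are used for the treatment of DED". If such events differ between arms, the subjects with week-6 values are no longer comparable groups. Section 10.5 sees this danger elsewhere: it plans no per-protocol analysis because treatment use might be related to outcome. Withdrawal followed by no further assessment can bring in the same selection through missing data.

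The conflict over drug non-compliance matters for the same reason, since it leaves open which subjects remain under observation.

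**Working it through.** **1. Which subjects lose their week-6 data**

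| Event | Stays in study? | Week-6 data under 7.7 |
|---|---|---|
| Inadequate control or severe disease (5.5, 8.1) | Yes, for ITT | Collected |
| Other concomitant regimen change (5.2) | Discretionary | Lost if withdrawn |
| Prohibited medication or procedure (5.2, 5.5) | Discretionary | Lost if withdrawn |
| IVCM at fewer than 2 of 3 visits (5.2) | No, mandatory withdrawal | No week-6 IVCM |
| Drug non-compliance | 5.2: yes; 10.5: discretionary | Unclear |

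Baseline IVCM is needed to judge eligibility (4.1, 4.2, 7.1). The imaging rule therefore reaches only subjects who missed both the week-2 and the week-6 images.

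**2. The plan's sample-size figure**

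Inputs from 10.3: d = 52 cells/mm², SD = 44, Z = 1.96. The displayed formula gives 4 × 44² × 1.96² / 52² = 29,749 / 2,704 = 11.0. The stated 22 per group is twice that. This mismatch is a separate matter; 22 per group (44 in total) is used below as stated. The allowance for loss is 50 − 44 = 6 subjects.

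**3. What replacement adds to power (dendritic-cell density only)**

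Two-sample t-test, two-sided alpha 0.05, noncentrality = 52 / (44 × √(2/n)):

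| n per arm | Noncentrality | df | Power |
|---|---|---|---|
| 25 | 4.18 | 48 | 98.4% |
| 22 | 3.92 | 42 | 96.9% |
| 19 | 3.64 | 36 | 94.3% |

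Replacing all 6 allowed losses (22 back to 25 per arm) gains 98.4 − 96.9 = about 1.4 points (0.9836 − 0.9692 = 0.0144). The planned between-group test is the Wilcoxon rank sum test, so these figures are a guide.

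**4. How far missing values could move the estimate**

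Assumptions, none from the documents: 25 randomised per arm, 3 missing in each, and missing subjects departing from their arm's mean by dA and dB, each between −44 and +44 cells/mm² (one planned SD).

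Shift in the difference = (3/25) × (dA − dB).

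- Equal departures in both arms: 0.
- Departure of 44 in one arm only: (3/25) × 44 = 5.3.
- Departures of 44 in opposite directions: (3/25) × 88 = 10.6, or 10.56/52 = 20% of the planned difference.
- All 6 losses in one arm, departure 44: (6/25) × 44 = 10.6.

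With 22 completers per arm, significance needs a difference of about 2.018 × 44 × √(2/22) = 26.8. With the standard error held there, a 10.6 shift could undo significance only for observed differences between 26.8 and 26.8 + 10.6 = 37.3 (unrounded 26.77 + 10.56 = 37.33).

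**The case against.** The strongest reply is that the plan already protects ITT where it matters most. Subjects with inadequate control or severe disease are expressly kept in, which removes much of the response-related loss. Investigators are masked, so discretion should not follow treatment arm. Both points carry weight. But the retention text does not cover every regimen change or prohibited treatment, and masking does not prevent withdrawal that follows response.

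Three stronger readings are tempting, and the documents do not support them.

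- *Replacement breaks ITT.* Section 10.5 analyses all subjects as randomised, and no text says that a new subject displaces a withdrawn one. Nor does the N/A in 10.4 leave the population undefined, because 10.5 defines both the ITT and the safety populations. What is missing is a sentence linking 5.2 to that definition.
- *Sections 5.5 and 8.1 contradict 5.2.* A specific statement that a subject will be kept can stand beside a general statement that a subject may be withdrawn. Which one governs should be stated, but this is not a direct conflict.
- *Replacement is unnecessary for power.* This can be shown only for dendritic-cell density. Section 10.1 also lists epithelial-cell and nerve measures as primary, and the documents give no effect size or SD for them.

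**Conclusion.** The concern holds as a gap between the stated primary analysis and the data the protocol will collect. Following 5.2, 5.5 and 7.7 as written loses week-6 outcomes that an already-planned visit could supply, and 10.5 has no firm rule for the resulting gaps. The conflict between 5.2 and 10.5 on drug non-compliance is direct. The replacement sentence needs clarification only.

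The size and direction of any bias are unknown, because the documents give no withdrawal rate, overall or by arm. A reader might infer from the 10.6 cells/mm² that the trial's conclusion is in danger. It does not show that: it rests on assumed one-SD departures in opposite directions, or on six losses in one arm, and even then a result at the planned 52 would remain significant. The change is worth making because it is cheap and because week-6 data not collected cannot be recovered later.

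**What to change.** 1. **Section 7.7.** Invite withdrawn subjects who still consent, and for whom the investigator sees no safety objection, to the week-6 assessments in 7.5. Include those data in the ITT analysis in the assigned arm. Apply this also to subjects who meet the 5.2 imaging rule, and keep any IVCM data they have. For subjects with baseline images only, the week-6 IVCM value will still depend on item 4.
2. **Section 5.2.** State that any added subject takes the next code in the 3.2.1 sequence and that no withdrawn subject is removed from the ITT set. No one then needs to know the withdrawn subject's arm.
3. **Reconcile.** Bring 5.2 and 10.5 into agreement on withdrawal for drug non-compliance, and say how 5.2 relates to the retention text in 5.5 and 8.1.
4. **Section 10.5.** Replace the optional imputation sentence with a pre-specified sensitivity analysis for missing week-6 dendritic-cell density. Use multiple imputation by arm from baseline and week-2 values, then shift the imputed values by 0, ±22 and ±44 cells/mm² (0, 0.5 and 1 planned SD), separately by arm and including opposite directions. Apply the between-group test to each completed data set and pool the results by a stated rule. For the other IVCM endpoints, express the shift as 0, 0.5 and 1 observed SD.
5. **Reporting.** Tabulate withdrawals by arm and reason.

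The planned ANOVA and Wilcoxon tests stay. The cost is some protocol wording, one already-planned visit asked of each withdrawn subject, and a little more analysis work.

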5.3 Study Drug Supplies

Both Lotemax and Soothe Tired Eyes Lubricant Eye Drop are commercially available from Bausch & Lomb Inc as eye drops.

Preparing and Dispensing

To mask the identity of the medication, the Massachusetts Eye and Ear Pharmacy will prepare, label and distribute both Lotemax and Soothe Tired Eyes Lubricant Eye Drop to the study participants.

Administration

Regardless of study drug assignment, each participant will self-administer one drop of the study medication to both eyes with the following regimen: 4 times a day for 2 weeks, 2 times a day for 2 weeks, and once daily for 2 weeks. The participants are being advised not to allow the dropper tip to touch any surface, as this may contaminate the medication.

Participants will be instructed on how to instill an eye drop at the baseline visit and will be asked to demonstrate application of an eye drop in front of research personnel to confirm that the appropriate technique is being used.

5.4 Study Drug/Device Storage and Accountability

The subjects will be instructed to store the medication at room temperature (15-25°C / 59-77°F) and to shake it vigorously before using it. If a subject contracts infectious conjunctivitis, they will be instructed to discard the remainder of the study drug. The subject will be scheduled for a clinic visit where an investigator will assess the severity of the infectious conjunctivitis as well as the subject's eligibility. If the investigator determines that the subject is still eligible, a new study drug will be sent from the host site pharmacy, Massachusetts Eye and Ear Infirmary, and given to the subject during their visit.

The participants will not be asked to return the unused drug following the completion of the study. Additionally, subjects who are withdrawn from the study will be asked

to discard the rest of their unused study drug. Therefore, the study drug will not be accounted for following dispensing and will not be destroyed by the MEEI pharmacy.

5.5 Other Medications

Administration

The use of any concurrent, prescription, or over-the-counter medication, is to be recorded along with the reason the medication was taken. During the study, all concomitant medication treatment regimens, ocular hygiene treatments (i.e., lid scrubs and warm compresses), or insertion of punctal plugs will be kept as constant as permitted by accepted medical practice.

Using artificial tears (preserved and non-preserved) are permissible at the screening visits and during the study. However, concomitant use of artificial tears will be monitored. At each study visit, subjects will be queried about the average number of times they used artificial tears each day during the past week and the number of days during the past week when they did not use any artificial tears.

Systemic and topical ophthalmic medications, that the subjects are already taking as part of their current treatment for dry eye disease will be maintained, without a change in frequency.

When necessary, treatment and administration of any other therapy, besides their current and study's regimen, will be done as the safety of the study participant is the primary consideration. The administration of a prohibited medication or procedure will be considered a protocol violation and the subject may be discontinued from the study. Prohibited medications include other ophthalmic steroids. Prohibited procedures include any ocular surgery.

• Rescue Medication or Therapy

When necessary, administration of any other therapy besides the study medication and their current medications will occur for the safety of the subject, which is the primary concern. If treatment with artificial tears is inadequate, or if the subject develops a severe form of ocular surface disease and dry eye, the subject may be unmasked by the investigator. To ensure the subject's safety and proper treatment, unmasking of the study treatment assignment will allow the investigator to institute appropriate follow-up care. The subject will be kept in the study so that we can do an "intention to treat" analysis.

6. BIOSPECIMEN COLLECTION (IF APPLICABLE)

- 6.1 Specimen preparation, handling, and shipping: N/A
- 6.2 Instruction for specimen preparation, handling and storage: N/A
- 6.3 Specimen shipment: N/A
- 6.4 Future use of stored specimens: N/A

7. STUDY PROCEDURES

7.1 Screening Procedures

Prospective participants, as defined by the inclusion/exclusion criteria, will be considered for entry into this study. Concurrent enrollment of subjects who are participants in other studies will be allowed based on the investigator's discretion.

During the consent process, study design and treatment regimen will be discussed with each subject. Written informed consent will be obtained before any study specific procedures are performed. However, standard of care clinical information (such as: medical history, TBUT, staining, and Schirmer's test) obtained during a subject's clinical visit within the previous 48 hours can be used during the screening visit to determine eligibility and as their baseline assessments. Additionally, standard of care IVCM images taken within a week of, or during, the subject's screening visit may be used to determine eligibility and as a baseline assessment.

The following evaluations and procedures will be performed for all subjects during the screening and baseline period:

- Written informed consent
- · Record of current ocular and systemic medications
- Record of significant medical/surgical history in the past 5 years
- · Record of demographic data, including date of birth, sex, and race/ethnicity
- Tear Break-up Time (TBUT)
- Eye examination (best corrected visual acuity, slit lamp biomicroscopy, applanation tonometry, funduscopy)
- · Corneal fluorescein staining
- · Conjunctival lissamine green staining

- · Schirmer's test with anesthesia
- · Central corneal in vivo confocal microscopy (IVCM)

Researchers will document type and frequency of artificial tear, ocular ointment, and other dry eye therapies use by the subject.

Subjects will start the study medication the first day after their screening visit, while continuing the use of their current medications.

Tear Break-Up Time (TBUT): The standard TBUT measurement will be performed by dropping of a fluorescein drop to the inferior tarsal conjunctiva. After several blinks, the tear film will be examined using a broad beam of the slit lamp with a blue filter. The time lapse between the last blink and the appearance of the first randomly distributed dark discontinuity in the fluorescein stained tear film will be measured three times and the mean value of the measurements will be calculated. The tear break-up time will be evaluated prior to the instillation of any eye drops and before the eyelids are manipulated in any way. Break-up times less than 10 seconds are considered abnormal. A positive change from baseline indicates improvement.

Corneal Fluorescein Staining (Appendix IV): Corneal fluorescein staining will be performed after 3 minutes of application of a fluorescein drop. The entire cornea will be then examined using slit-lamp evaluation with cobalt blue illumination. Staining will be graded using the NEI grading scheme, with a total range of 0-15.

Schirmer's Test with Anesthesia: The Schirmer's test will be performed 3 minutes after a drop of topical anesthesia with 0.5% proparacaine (Alcon Inc., Ft Worth TX) is

applied to the eye. The Schirmer test is performed by placing a narrow filter-paper strip (5 x 35 mm strip of Whatman #41 filter paper) in the inferior cul-de-sac. This test is to be conducted in a dimly lit room. The subject should gently close their eyes until five minutes have elapsed and the strips are removed. Since the tear front will continue advancing a few millimeters after it has been removed from the eyes, it is important to mark the tear front with a ball-point pen at precisely five minutes. Aqueous tear production will be measured by the length in millimeters that the strip wets during 5 minutes.

Conjunctival Lissamine Green Staining (Appendix IV): Grading of conjunctival lissamine green staining will be performed after 2 minutes of application of a lissamine green drop. The nasal and temporal conjunctiva will be examined using slit-lamp evaluation with white light. Staining will be graded using the NEI grading scheme, with a total range of 0-18.

In Vivo Confocal Microscopy (IVCM):

In vivo confocal microscopy (IVCM) is a new imaging method which allows visualization of the corneal structures at the cellular level. With a magnification of 800 times, it makes it possible to detect and quantify changes in the epithelial layers and sub-basal nerve plexus. With this technology, size and reflectivity of superficial epithelial cells, as well as the number of immune dendritic cells (DC) can be readily evaluated.

This is a contact imaging procedure and therefore a drop of topical anesthesia will be used for both eyes. A topical gel is applied to the imaging cap as well as the subject's eye to provide a coupling medium between these two surfaces. Three to four locations in the central part of the cornea will be imaged at the depth of the superficial epithelium and sub-basal layer which is 50 to 80 microns deep. A sequence of 100 images will be obtained.

7.2 Enrollment/Baseline Procedures

The baseline visit may occur immediately after the screening assessments. Following the baseline assessments, subjects will be randomized into a treatment group. If an individual is deemed eligible to participate, the following baseline procedures will be performed:

• Symptom Assessment iN Dry Eye (SANDE) questionnaire:

SANDE Questionnaire (Appendix III): The Symptom Assessment in Dry Eye (SANDE) questionnaire utilizes a 100-mm horizontal visual analog scale (a 100mm line) to quantify subject symptoms of ocular dryness and/or irritation. In the SANDE symptom questionnaire-I, subjects will be asked to put a mark on two given lines to depict the extent of their dry eye symptoms separately in terms of frequency and severity. At the screening visit and all follow-up visits, the SANDE symptom questionnaire-I will be administered. At each follow-up visit, the SANDE symptom questionnaire-II will be also administered. To indicate whether there are any differences in symptoms from the previous visit, subjects will compare the frequency and severity of their current level of symptoms with the level at their previous visit by placing a mark to the left of central anchor (if less than previous visit) or to the right of central anchor (if more than the previous visit), according to how much of a change they perceive. The location of the mark made by the subject for each question of the SANDE-I will be measured in mm from the left-hand side of the 100 mm line, and the number will be recorded in mm. For the second version of the questionnaire SANDE-II, the distance between the mark made by the subject and the central anchor will be measured and it will be recorded as a negative value if to the left of the central anchor and as a positive value if placed to the right of the central anchor. Then a global score will be calculated by multiplying the frequency score by the severity score and taking the square root of the result to transform back to the original centesimal scale.

• Ocular Surface Disease Index (OSDI) questionnaire:

OSDI Questionnaire (Appendix II): 12-item questionnaire designed to provide a rapid assessment of the symptoms of ocular irritation consistent with dry eye disease and their impact on vision-related functioning. The 12 items of the OSDI questionnaire are graded on a scale of 0 to 4, where 0 indicates none of the time; 1, some of the time; 2, half of the time; 3, most of the time; and 4, all of the time. The total OSDI score is then calculated on the basis of the following formula: OSDI=[(sum of scores for all questions answered) $\times 100$]/[(total number of questions answered) $\times 4$].

